1.3 Summary of PATHWAYS Research Programme

The PATHWAYS research programme includes five inter-related studies designed to increase our understanding of gender incongruence amongst CYP and its longitudinal course. The full programme is outlined here to provide context for PATHWAYS TRIAL, PATHWAYS HORIZON INTENSIVE and CONNECT, which are the subject of this protocol.

All the PATHWAYS workstreams, bar PATHWAYS Engagement, involve CYP and their parents/carers/legal guardians who are attending the NHS Gender Services for Children and Young People (CYPGS).

The overarching aims of the PATHWAYS research programme are:

- 1) To determine the short/medium-term benefits and risks of GnRHa for puberty suppression, across psychosocial, physical, cognitive and brain outcomes, in CYP with gender incongruence.
- 2) To understand the care needs and experiences of CYP with gender incongruence that are associated with using GnRHa or not through longitudinal quantitative and qualitative studies.
- 3) To continue to involve CYP with gender incongruence and their parents/carers/legal guardians in designing, implementing and interpreting the research to ensure this study addresses their needs and can inform planning and data collection in any longer-term follow-up.

Studies within the PATHWAYS Programme:

1.3.1 PATHWAYS HORIZON

PATHWAYS HORIZON is an observational cohort (n~3600) of all CYP attending the CYPGS. HORIZON participants will be asked to complete questionnaire measures about their experiences, mental health, and quality of life on an annual basis throughout the course of the study. The study will last for the duration of the funding period (5.5 years).

1.3.2 HORIZON INTENSIVE

In addition, we will recruit 300 CYP to HORIZON INTENSIVE. HORIZON INTENSIVE participants will be recruited from the HORIZON cohort and will be broadly matched to those participating in TRIAL (below) on clinical centre, birth-registered sex, presence of a neurodevelopmental disorder or high level of traits and chronological age. They will be asked to complete all the same measures as PATHWAYS TRIAL including the physical health assessments except that physical health, cognitive and brain imaging measures will only be undertaken at baseline and endpoint. The PATHWAYS HORIZON INTENSIVE protocol is included in the PATHWAYS TRIAL protocol and application.

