Intervention (Description, frequency, details of delivery)	
Decapeptyl® SR (long-acting formulation of Triptorelin) 22.5mg injections.
 
Administration: Intramuscular injections every six months at 0, 6, 12, 18 and 24 months post-randomisation. Option to move to 3-monthly or 1-monthly injections based on clinical grounds.
 
Monitoring: Regular follow-up appointments to assess efficacy and safety, including monitoring hormone levels and physical development. Routine blood tests, DEXA scans, and physical assessments (height, weight, BMI, blood pressure, and puberty staging). Psychosocial screening to identify any unmet needs and escalate these to appropriate services.

Comparator Intervention:	
Delayed Start: Participants in the delayed start group will be offered GnRHa treatment one year after randomisation. They will receive the same monitoring and assessments as the immediate start group.

Maximum Duration of Treatment of a Participant:	
24 months in randomised trial with potential for non-randomised open extension according to clinical compassionate care.

Study Synopsis

Title Of Clinical Trial:	Puberty Suppression And Transitional Healthcare with Adaptive Youth Services (PATHWAYS): PATHWAYS HORIZON INTENSIVE
Protocol Short Title/ Acronym:	PATHWAYS HORIZON INTENSIVE
Study Phase:	Observational
Sponsor Name(s):	King's College London South London and Maudsley NHS Foundation Trust
Chief Investigator(s):	[name] [name] (Deputy CI)
Medical Condition or Disease Under Investigation:	Gender Incongruence
Purpose of Study:	To provide a non-randomised control group of CYP with gender incongruence not receiving GnRHa who will be compared to TRIAL participants with respect to outcomes.

The electronic version of this document is the latest version. It is responsibility of the individual to ensure that any paper material is the current version. Printed material is uncontrolled documentation.

Primary Objective:	To provide a naturalistic comparison to participants in TRIAL with respect to benefits and risks of GnRHa over 24 months. Participants will be assessed with the same measures of possible benefit and harms as for TRIAL.
Secondary Objective(s):	To compare the priority goals of CYP with gender incongruence not receiving GnRHa to those in TRIAL To track the trajectories of cognition in CYP who are not receiving GnRHa
Primary Outcome Measure	KIDSCREEN-10 health-related quality of life questionnaire

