As each participating CYP reaches endpoint, they will decide, with their parents/legal guardians and health-care professionals, including paediatric endocrinology, what further interventions, if any they wish to pursue. This may include remaining on GnRHa, moving to cross-sex hormones, or stopping/pausing GnRHa.

HORIZON INTENSIVE is a non-randomised comparison group of CYP not receiving GnRHa who are broadly matched on key participant characteristics. They will complete the same physical, physiological and cognitive measures as TRIAL participants, although only at baseline and endpoint. As CYP who experience gender incongruence may differ from the general population of same-aged CYP, these data will provide a comprehensive comparison to aid interpretation of the effects of GnRHa.

PATHWAYS CONNECT is a magnetic resonance (MR) brain imaging study to examine whether the use of GnRHa alters the trajectories of brain development. PATHWAYS CONNECT will recruit a subset of CYP enrolled in Trial and HORIZON INTENSIVE to participate in serial brain imaging over the same two-year time course.

The electronic version of this document is the latest version. It is responsibility of the individual to ensure that any paper material is the current version. Printed material is uncontrolled documentation.

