# Not required if already captured as part of PATHWAYS HORIZON ## At baseline and Month 24 only for HORIZON INTENSIVE participants * All ongoing forms to be reviewed and updated at each visit ** Tanner staging optional at Months 12, & 24 for immediate GnRHa participants; Month 24 optional for delayed GnRHa participants ***Safety review including vital signs, adverse event reporting, concomitant medication review, pregnancy test (POCBP only) at every injection visit for participants switching to 3-monthly or monthly IMP preparation.											+ Baseline and 24 months only for HORIZON INTENSIVE participants ++ People of child bearing potential only +++ Dispensing at Months 9,15,21 if changing to 3 monthly preparation ^ Bone age scan at M12 & M24 optional ^^ Visit window for final scan of 6 weeks prior to/following final treatment injection ^^^Gender Identity Questionnaire completed only at baseline for Parents ### Ongoing questionnaires and DEXA scans completed annually during follow up period

Table 2. Schedule of events

The electronic version of this document is the latest version. It is responsibility of the individual to ensure that any paper material is the current version. Printed material is uncontrolled documentation.

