4.2.3 CONNECT

For MRI scans, baseline scans must be undertaken prior to the first injection. For delayed-start participants, this also applies to their scan at midpoint, i.e., before their first injection. Otherwise, scans should be within a four week window either side of the midpoint or endpoint date.

Cognitive assessments will ideally take place on the same date as the baseline, midpoint and endpoint injection but otherwise the windows of four weeks either side apply.

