13.5.1.2 HORIZON INTENSIVE

The primary outcome for HORIZON INTENSIVE is the KIDSCREEN-10. Analysis will be carried out in the same fashion as the Horizon trial, using a Bayesian linear mixed model within a Bayesian framework. Stratifying factors will be used as fixed effects and participant will be used as a random effect to allow for the clustered nature of repeated measures data. Priors will be uninformative. As the HORIZON INTENSIVE cohort is loosely matched to trial participants, this matching will be taken into consideration.

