13.5.2.1.2 HORIZON INTENSIVE

Continuous secondary outcomes will follow the same analysis plan as the primary analysis.

13.5.2.2 *Binary outcomes*

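### At month 24 the TRIAL v HORIZON INTENSIVE comparison of cognitive tests sets a third sitting against a second, so practice is fully confounded with cohort and could mask cognitive harm

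*Protocol*

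**What the plan says.** Both randomised arms take the cognitive battery three times. Protocol 4.2.3 says "Cognitive assessments will ideally take place on the same date as the baseline, midpoint and endpoint injection", and Tables 2, 4 and 5 mark WISC-V, D-KEFS, CHAMP, MVP and BRIEF at baseline, month 12 and month 24.

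HI takes the same battery twice. Section 1.3.2 has HI complete the TRIAL measures "except that physical health, cognitive and brain imaging measures will only be undertaken at baseline and endpoint". Section 2 (Trial Design) repeats this: "They will complete the same physical, physiological and cognitive measures as TRIAL participants, although only at baseline and endpoint". The legend to Table 2 says "Baseline and 24 months only for HORIZON INTENSIVE participants", and Table 6 has no month-12 mark for any cognitive test. The schedule is consistent throughout.

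The HI synopsis gives the cohort its purpose, "To provide a naturalistic comparison to participants in TRIAL with respect to benefits and risks of GnRHa over 24 months", and lists as a secondary objective "To track the trajectories of cognition in CYP who are not receiving GnRHa".

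The model is given in section 13.5.1.2: "Stratifying factors will be used as fixed effects and participant will be used as a random effect". Section 13.5.2.1.2 extends it: "Continuous secondary outcomes will follow the same analysis plan as the primary analysis". The cognitive assessments are among the HI outcomes (13.2.5). The protocol does not mention practice or retest effects, alternate forms or the number of sittings.

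**The concern.** Scores on performance tests can rise because the child has met the tasks before. Here the cohorts differ in two ways at month 24: TRIAL has had one more sitting, and its last one was more recent. Both would tend to lift TRIAL relative to HI.

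Cognition is named in the primary objective (2.4.1). Section 2.2 groups it, tentatively, with effects that may build up as puberty is suppressed for longer. It also notes that the pre-post IQ studies it cites span more than two years and leave the timing of change unclear. The randomised comparison of GnRHa with no GnRHa exists only up to month 12, because the delayed arm is then offered treatment. The immediate arm against HI at month 24 is therefore the only planned contrast of about two years of drug with none, and the imbalance falls on it. The stake is a falsely reassuring, or falsely favourable, statement on two-year cognition.

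**Working it through.** **1. Sittings by month 24**

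| Cohort | Sittings | Gap before the month-24 sitting |
|---|---|---|
| TRIAL, immediate | 3 (months 0, 12, 24) | 12 months |
| TRIAL, delayed | 3 (months 0, 12, 24) | 12 months |
| HI | 2 (months 0, 24) | 24 months |

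Within TRIAL the arms are balanced: second v second sitting at month 12, third v third at month 24. TRIAL v HI at month 24 is third v second. HI does have one retest, so what differs is the third-over-second increment plus any effect of the shorter gap.

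**2. Can the stated model separate this?** No. As scheduled, every TRIAL participant has three sittings at month 24 and every HI participant two, so a covariate for sittings would be collinear with cohort. Every scheduled third sitting also falls in an arm assigned to GnRHa by then, so the third-sitting gain cannot be estimated apart from drug. Matching on site, sex, age and neurodevelopmental status does not touch it, and age-standardised scores remove development but not practice.

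**3. Which measures?** WISC-V, D-KEFS and CHAMP. The BRIEF is rated by the parent (4.13.5) and the MVP checks validity (4.13.4).

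**4. Size, as an illustration only.** The documents give no practice gain, so p, the extra gain in SD units, is assumed to range from 0 to 0.3.

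Plan figure: section 13.4.2 states a detectable effect of 0.42 SD for 300 v 112 with the equivalent of 90% power. It gives no alpha or dropout for this.

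- Check, normal approximation, two-sided 5%, no dropout: (1.96 + 1.2816) × √(1/300 + 1/112) = 3.2416 × 0.1107 = 0.359.
- With 25% loss in both groups: 0.415, close to the stated 0.42.

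Taking 0.42 at 90% as stated, the implied standard error is 0.42 / 3.2416 = 0.130. With a true decline of 0.42 the expected observed decline is 0.42 − p, so z = 3.2416 × (0.42 − p) / 0.42 and power = Φ(z − 1.96).

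| p (SD, assumed) | z | Power, stated 0.42 at 90% | Power, no dropout |
|---|---|---|---|
| 0 | 3.242 | 90% | 97% |
| 0.1 | 2.470 | 70% | 82% |
| 0.2 | 1.698 | 40% | 51% |
| 0.3 | 0.926 | 15% | 19% |

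The last column uses the standard error 0.1107. The level depends on the dropout assumed, but the steep fall does not. With no true effect, the same p would appear as a difference in favour of TRIAL.

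The 300 v 226 comparison in 13.4.2 is not used, because the pooled trial group includes a delayed arm with only one year of drug at month 24.

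**The case against.** **HI is openly non-randomised.** Section 1.5 warns that observational estimates are often biased, the synopsis calls the comparison naturalistic, and section 2.2 makes the randomised midpoint the test of GnRHa against none. This stands as to the hierarchy of evidence. However, practice is a bias added by the protocol's own schedule, and section 13.5 says nothing to limit what may be concluded from the cognitive contrast with HI.

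**Handling of practice belongs in the SAP.** This stands in part: a sensitivity analysis may properly be set out there. But the protocol itself fixes both the schedule and the model, and applying the primary model unchanged to cognition produces the confounded contrast. No covariate added later removes it.

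**The size is assumed.** This stands fully. The increment could be near zero, which is why the range starts at 0. The planned summary is a posterior mean with a 95% credible interval, and the protocol states no decision rule for cognition, so the power figures are a yardstick only.

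**The direction.** A reader might infer that the month-24 contrast is biased towards no harm, full stop. The documents do not support that. HI members do not want GnRHa or are judged unsuitable for it (3.3), so selection differences of unknown sign also act. Only the practice component has a predictable sign. A reader might also infer that practice gains arise in the treated group alone, but HI has a retest too.

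**Conclusion.** The point holds for the month-24 comparison of TRIAL with HI on WISC-V, D-KEFS and CHAMP. The number of sittings (three v two) and the last retest gap (12 v 24 months) are fully confounded with cohort, and following the plan as written leaves any extra practice gain inside the estimate. That gain can mask cognitive harm or suggest benefit. Whether it does, and the net direction once selection is counted, cannot be known from the documents.

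On the stated 0.42 SD at 90% power, an assumed gain of 0.1 to 0.3 SD would cut power for a true 0.42 SD decline to between 70% and 15%; a gain of 0 leaves it at 90%. This rests on a normal approximation, a two-sided 5% reading of equivalent power, and a range for the gain that is an assumption.

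It would go too far to say that the trial cannot assess cognition. Both randomised contrasts are balanced, and month 12 remains a fair test of one year of GnRHa against none. The primary outcome and the BRIEF are untouched. The matter is worth correcting because it changes what may be said about two-year cognitive safety.

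**What to change.** Amend section 13.5, with detail in the SAP if preferred:

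1. State that for the performance-based cognitive tests the randomised contrasts carry the causal conclusions, with month 12 as the comparison of GnRHa with none.
2. Report the month-24 TRIAL v HI contrast as confounded by number of sittings. Add a sensitivity analysis that subtracts a range of practice increments, including 0, from TRIAL month-24 scores, test by test, and gives the increment at which the conclusion changes. For example, with a standard error of 0.130 SD and an observed difference of 0, the adjusted interval would exclude no decline once the increment passes 1.96 × 0.130 = 0.25 SD.
3. Report the delayed arm's untreated change from baseline to month 12 on age-standardised scores as a rough guide to first-retest gain. It is not the third-over-second increment, and it also carries a year of development and any reaction to being allocated to delay.

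TRIAL at month 12 against HI at month 24 matches the number of sittings but may be shown only as supplementary. It has at most 12 months of drug against 24 months without, and the retest gaps remain unequal, so it neither removes nor bounds the bias.

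Cost: a little more analysis and a less definite two-year cognitive statement. No visits change. A month-12 sitting in HI, for all or a subset, would address the imbalance directly, but it adds participant burden and is not needed for this minimum correction.

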1.3.3 PATHWAYS TRIAL

PATHWAYS TRIAL is a trial of GnRHa in the management of gender incongruence in children and young people.

1.3.4 PATHWAYS CONNECT

PATHWAYS CONNECT looks at outcomes relating to cognition and brain development in CYP attending the services, including those who are and are not receiving GnRHa.

The electronic version of this document is the latest version. It is responsibility of the individual to ensure that any paper material is the current version. Printed material is uncontrolled documentation.

[figure not shown]
1.3.5 PATHWAYS VOICES

PATHWAYS VOICES uses longitudinal qualitative interviews to explore the needs and care experiences of CYP and their families and how these change over the course of time / treatment.

1.3.6 PATHWAYS ENGAGEMENT

PATHWAYS ENGAGEMENT is an advisory group of young adults >18 years, adults with gender incongruence, and parents/carers/legal guardians who will advise on all aspects of the programme, including outcome measures, patient involvement in research and strategies for long-term patient engagement, interpretation, and communication of findings. Members of PATHWAYS ENGAGEMENT will meet in person in London and/or online for briefer meetings. NB: As an advisory group of experts by experience, ethical approval will not be sought.

1.4 Relationship between PATHWAYS studies

* Those discharged by the service will only be eligible for HORIZON(observational) and would not be eligible for Trial, CONNECT, HORIZON Intensive or VOICES

Figure 2. Overlap between PATHWAYS participants in different studies

Table 1. Relationship between PATHWAYS protocols and participant groups

Study Protocol	Participant group		
	Trial immediate start	Trial delayed start	HORIZON INTENSIVE
Trial	113	113	300
CONNECT	75 of 113	75 of 113	100 of 300

All CYP attending the CYPGS will be eligible for PATHWAYS HORIZON. We anticipate ~80% of CYP will assent/consent to HORIZON. Only CYP who assent/consent (and provide parental consent) to PATHWAYS HORIZON will be approached for PATHWAYS HORIZON INTENSIVE. Many CYP subsequently deemed eligible for and enrolling in PATHWAYS TRIAL will first be members of PATHWAYS HORIZON. Once they join PATHWAYS TRIAL, they will become part of that study and data collection will follow that protocol (rather than the PATHWAYS HORIZON protocol). CYP attending the CYPGS who decline participation in HORIZON but are deemed eligible for PATHWAYS TRIAL may join that study once they provide assent/consent. CYP participating in PATHWAYS VOICES are drawn from those in PATHWAYS HORIZON considering GnRHa (and hence may become members of TRIAL). **Figure 2** depicts the relationship and participant overlap between studies.

1.5 Rationale for a Randomised Controlled Trial

RCTs are the gold standard method to determine the causal role of any treatment in relation to observed benefits and harms⁹. While observational studies have been used to explore efficacy and side effects, it is well-recognised that the estimates arising from such studies are often biased (usually but not always in favour of increased efficacy and fewer adverse effects) because of patient selection and inability to fully account for confounding effects. In gender medicine and studies of GnRHa, a common confounder is the co-occurrence of psychosocial and endocrine care where specific effects cannot be determined out in observational studies. While the pre-eminence of RCTs is generally well-recognised, due to the controversial nature of this intervention and research in this field, the scientific and ethical rationale for an RCT is outlined here.

1.5.1 Clinical equipoise

The ethical basis of all RCTs is clinical equipoise, that is, the balance of benefits and harms of an intervention is uncertain and reasonably balanced between the intervention arms. While many claims have been made about benefits and harms of GnRHa, depending on the perspective of the proponents, a recent systematic review of interventions to suppress puberty⁷ highlighted the general low- to medium-quality of the available evidence. No previous RCTs were identified. In particular, in relation to mental health, psychosocial functioning and quality of life there was inconsistency

The electronic version of this document is the latest version. It is responsibility of the individual to ensure that any paper material is the current version. Printed material is uncontrolled documentation.

among studies showing either some improvement or no change with initiation of GnRHa. With regard to possible physical harms, studies show decreased age-standardised bone mineral density with GnRHa; however, there is an absence of follow-up to determine whether these changes are persistent after ceasing GnRHa and/or commencing on gender affirming hormones. There has been speculation about cardiovascular harms, but there is no evidence to support this.

1.5.2 Retrospective studies.

Retrospective studies are a form of observational study looking at earlier data in a cohort of individuals. They are used to identify potential causal factors that can be formally tested in more rigorous designs. Retrospective studies have all the drawbacks of prospective observational methods, outlined above. They also require that relevant data were collected at earlier timepoints.

It has been suggested that UK research on GnRHa for puberty suppression in gender incongruence might start with a retrospective study of the young people previously seen at the Tavistock Service who are now young adults. It would not be possible to address important questions about GnRHa for several reasons. First, clinically recorded information on this patient cohort was not standardised or recorded at specific timepoints. Second, published reports from this cohort suggest high levels of attrition which are likely to be biased in relation to clinical outcomes. Third, some important classes of data, including cognition, childhood adverse experiences and neurodiversity, were not recorded at all. Hence, we conclude that a retrospective study would not provide alternative evidence.

1.5.3 Must the research be undertaken with children and young people, who are a vulnerable population?

Ethical considerations dictate that research should only involve vulnerable populations such as children and young people when the research question cannot be adequately addressed with an alternative population or study design. In this instance, suppressing puberty as a component of intervention for gender incongruence can only be performed during puberty, limiting it to adolescents. While due care and attention should be applied when considering research in children and young people, we also note that the failure to undertake research has disadvantaged their health. For example, cancer outcomes in young people lagged behind those in adults until there was a concerted effort to develop and test new interventions for childhood cancers.^{10, 11}

